information. Qualifying providers will be recruited for the study and will be formally consented. The enrolled providers will be randomized to treatment and control groups (using the OneSheet vs. NOT using the OneSheet). The participating providers that have been randomized to the treatment group will be given instructions on how to access and use the OneSheet when treating patients' chronic pain. These providers will also be given ongoing technical support and assistance with integrating the OneSheet into their clinical workflows. Those participating providers who have been randomized to the control group will not be given any information or instructions on accessing and using the OneSheet. At Eskenazi, when a qualifying patient, identified by Regenstrief through an algorithm developed in collaboration with the researchers, comes to a visit with a participating provider in the treatment group, a BPA will appear in the patient's record, alerting the provider to consider utilizing the OneSheet for that patient's chronic pain management during the visit. Eskenazi will share the MRNs of qualifying patients, and dates of qualifying visits with Regenstrief Data Core, who will collect outcome measure data, remove patient identifiers (with the exception of dates), and share this limited data set with the research team for analysis. At Wake Forest, when a qualifying patient, identified through the same process, comes to a visit with a participating provider in the treatment group, a BPA will appear in the patient's record, alerting the provider to consider utilizing the OneSheet for the patient's chronic pain management during the visit. Wake Forest Baptist Health will share the MRNs of qualifying patients, and dates of qualifying visits with an honest broker, who will collect outcome measure data, remove patient identifiers (with the exception of dates), and share this limited data set with the research team for analysis. At both sites, formal informed consent and HIPAA authorization will not be obtained from qualifying patients being treated by participating providers.

q23358

Will any non-English study documents be uploaded?

No

q24919

Is this research funded by, or has a funding application been submitted to, a federal agency? This includes federal pass- through funding.

Yes

q23234

List inclusion criteria - eligibility criteria for subjects.

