to answer subjects' questions. Any questions they are not able to answer, the investigator will refer the subject to the PI.

q931

Does the research include any minimal risk procedures to which subjects will not consent?

No

q23678a

For those subjects who will consent to participate, choose whether the consent process will be documented by a written signature from subjects.

All consented subjects will provide a written signature as documentation of consent.

q30129a

Will subjects participate in any study activity prior to physically signing a consent document?

No

q940a

Explain the process for obtaining a written signature from subjects.

Clinician participants will be informed about the study, and provided a copy of the consent statement. A member of the research team will go over the sections of the informed consent statement with the potential subject and then allow time for questions and clarifications. If this occurs in person, the potential subject may choose to sign the paper informed consent statement at that time. If this occurs remotely, the potential subject will be directed to the REDCap form where they may choose to electronically sign the consent statement. For clinicians who do not sign the consent statement at the initial contact, the study team will attempt to contact to recruit and consent a potential participant no more than 5 times, or until they state they do not want to participate.

q23764

Since some subjects will not consent to participation in the research, a waiver of consent is required. Choose the appropriate reason for waiving consent.

Research is minimal risk and obtaining consent is not practicable.

q904b

Explain how the research involves no more than minimal risk to the subjects.

The collection of outcome data is only meant to identify physicians who will be the subjects on whom we are actually collecting data. The physicians will be consented.

q906b

Explain how the waiver will not adversely affect the rights and welfare of subjects.

The identity of the patients will not be known by the study team. It is only meant to identify physicians. Data will not be used in any other way.

q907b

Explain how the research could not be practicably carried out if informed consent were required.

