9/16/20	Individual randomization instead of clinic level, updated ICF total number of participants - a005
8/6/21	Adding second recruitment at both sites to increase sample size due to provider turnover-v5

Administrative Details Form

Protocol Details

9031

Protocol Type

Expedited

Billing Account #

Study Status

Submission Details

9000

Submission Review Level

Expedited

9030

Expedited Category.

Category 5: Data or specimens that have been or will be collected for nonresearch purposes

Category 7: Survey, interview, focus groups, human factor, group behavior or characteristics

9002

Criteria for Approval. Select to confirm.

Approved: The criteria for approval of the research are satisfied in accordance with IU HRPP Policies, and applicable federal regulations.

Protocol Determinations

9003

Protocol Level of Risk.

Minimal risk

9020

Is renewal required for this research?

No

9004

Check all determinations that need to be made.

Informed Consent Waiver

HIPAA Waiver

Certificate of Confidentiality

9005

Informed Consent Waivers

Waiver of informed consent granted in accordance with IU HRPP Policies

9006

HIPAA Waivers

Participation

9010

Brief description of PHI - Participation

Patient demographics Healthcare encounter location, type, provider, and date

Chronic pain diagnosis and date Patient goal type and date Pain and function

assessment (PEG) results and date of assessment PDMP check completion

date Laboratory, procedure, medication, and referral orders Opioid risk tool

results and date of assessment Patient MRN

9009

Participation HIPAA Waiver

Waiver of authorization criteria satisfied in accordance with 45 CFR 164.512(i) (2)(ii). Waiver of authorization approved in accordance with 45 CFR 164.512(i).

9025

Certificate of Confidentiality.

The research is subject to the NIH Policy for Issuing Certificates of Confidentiality and therefore has been issued a Certificate.

9028

Other Determinations.

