**Nudging Primary Care Providers toward Guideline-Recommended
Opioid Prescribing through Easier and More Convenient EHR
Information Design**

R33 Clinical Trial
MPIs: [name] and [name]

NCT04295135

IRB #1911922583

Mar 5, 2024

CT. Gov: Statistical Analysis Plan

Study title: Nudging Primary Care Providers toward Guideline-Recommended Opioid Prescribing through Easier and More Convenient EHR Information Design

To assess the OneSheet effects on guideline-concordant care, we collected data from participating clinicians' visits with patients meeting several criteria described below. The criteria were: 1) 18+ years old; 2) no cancer diagnosis in the prior 3 years; 3) meet the following indications of chronic pain over the most recent 24 months:

- a. 3+ unique* instances of a qualifying pain diagnosis (either billed diagnosis or problem list) OR
- b. 3+ unique* prescriptions for one or more of the following drugs: an opioid ("opioid agonist," "opioid partial agonist," "opioid combinations"), Tramadol, Nortriptyline, Amitriptyline, Gabapentin, Pregabalin, Duloxetine, desipramine, milnacipran, tapentadol OR
- c. 2 unique* instances of a qualifying pain diagnosis AND 2+ unique* pain medication prescriptions containing one or more of the drugs listed in b.

*"unique", for Diagnoses and medications was defined as separated by at least 30 days from any previous qualifying diagnosis or prescription.

Because chronic pain treatment is often discussed during visits not explicitly identified as related to chronic pain, any visit that a qualifying patient has with a participating primary care clinician was considered as a qualifying visit for the trial. The data for qualifying visits was collected one year before OneSheet access was granted (October/November 2019) to May 2022 (18 months of the trial period).

Outcomes: We constructed six visit-level binary outcomes that could be measured with electronic health record (EHR) data and reflected recommendations in the 2016 CDC opioid prescribing guideline: 1) recording pain-related goals in the last 90 days; 2) recording pain and function via the Pain, Enjoyment, and General (PEG) assessment in the last 90 days; 3) checking the prescription drug monitoring program (PDMP) in the last 90 days; 4) assessing UDS results in the last calendar year; 5) ordering medications for opioid use disorder (MOUD) within seven days of the visit; and 6) ordering Naloxone within seven days of the visit.

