Statistical Analysis: We used descriptive statistics to compare the demographic characteristics of clinicians assigned to the intervention group versus the control. We computed our outcomes at the patient-visit level for visits by qualifying patients with study providers for the 12 months before the OneSheet went live (the baseline period) and 18 months following OneSheet go-live. We excluded patients from the sample who had visits during the study period with both treatment and control clinicians to ensure that outcomes were not compared across trial arms for the same patient. To estimate the effect of OneSheet on our outcomes, we used a multi-level linear probability model including patient demographics, clinician random effects, and indicator variables for a) site; b) treatment and control clinicians; and c) pre-/post-OneSheet go-live. We included an interaction term for treatment and post-OneSheet go-live, the coefficient for which estimates the causal effect of OneSheet on our outcomes of interest. Statistical tests were 2-tailed, and p-values < 0.05 were considered statistically significant. Data analyses were performed from November 2022 to September 2023 using *tidyverse*, *lubridate*, *fixest*, and *lme4* R packages in RStudio (Bates et al., 2015; Berge, 2018; Grolemund et al., 2011; Wickman, 2017).

References:

Agency for Healthcare Research and Quality, 2018. Recommendation 7: Opioid therapy risk assessment. Retrieved March 1, 2024, from
<https://cds.ahrq.gov/cdsconnect/artifact/recommendation-7-opioid-therapy-risk-assessment>

Wickham H. The tidyverse. R package ver 1 1 1 [Internet]. 2017; Available from:
https://slides.nyhackr.org/presentations/The-Tidyverse_Hadley-Wickham.pdf

<https://www.jstatsoft.org/v40/i03/>

Bergé L (2018). “Efficient estimation of maximum likelihood models with multiple fixed-effects: the R package FENmlm.” CREA Discussion Papers.

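### The SAP dates the post period from OneSheet go-live for every clinician, so visits that second-wave treatment clinicians made before their own randomisation would count as treated

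*SAP*

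**What the plan says.** The SAP's Statistical Analysis paragraph takes visits with study providers "for the 12 months before the OneSheet went live (the baseline period) and 18 months following OneSheet go-live". The model has clinician random effects, patient demographics and "indicator variables for a) site; b) treatment and control clinicians; and c) pre-/post-OneSheet go-live". The coefficient on treatment by post is presented as the causal effect of OneSheet. No enrolment, randomisation or access date for the individual clinician enters the model.

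The SAP's opening section sets the data window as "one year before OneSheet access was granted (October/November 2019) to May 2022 (18 months of the trial period". It also says that "any visit that a qualifying patient has with a participating primary care clinician was considered as a qualifying visit for the trial". Neither statement separates visits made before a clinician joined from visits made after.

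The Protocol's IRB Amendments table has an entry dated 8/6/21: "Adding second recruitment at both sites to increase sample size due to provider turnover". On exposure, the Protocol's description of research interventions says: "The participating providers that have been randomized to the treatment group will be given instructions on how to access and use the OneSheet". The best-practice alert likewise fires only at visits with a participating treatment-group provider. Under Informed Consent the form asks: "Will subjects participate in any study activity prior to physically signing a consent document"; the answer is No. The SAP does not mention a second recruitment.

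**The concern.** A clinician recruited after August 2021 and randomised to treatment had no OneSheet instruction, support or alert in the months between go-live and joining. If that clinician was already seeing qualifying patients at a study clinic, those visits fall in the SAP's post period and carry the treatment label. The interaction term then averages exposed and unexposed time.

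The consequence is dilution: a real effect on any of the six outcomes could be understated or missed. Dilution of this kind does not by itself create a false positive. The SAP does not let a reader tell whether such visits were in the data.

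**Working it through.** **Inputs.** Window start October/November 2019, end May 2022, 12 months of baseline and 18 months post (SAP). Second recruitment approved 6 August 2021 (Protocol, IRB Amendments). The documents do not give the number of second-wave clinicians, their arms, their join dates or their earlier visits.

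**Reproducing the plan's figure.** November 2019 + 12 months = November 2020; November 2020 to May 2022 = 18 months, which matches. An October 2020 go-live gives 19 to 20 months, so I carry a range of dates.

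**Fraction of the post period before the second recruitment (f).** f = (go-live to 6 August 2021) ÷ (go-live to data end), in months:

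| Go-live | To 6 Aug 2021 | To 1 May / 31 May 2022 | f |
|---|---|---|---|
| 1 Oct 2020 | 10.15 | 18.96 / 19.94 | 0.536 / 0.509 |
| 1 Nov 2020 | 9.13 | 17.94 / 18.92 | 0.509 / 0.483 |
| 30 Nov 2020 | 8.18 | 16.99 / 17.97 | 0.482 / 0.455 |

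So f runs from 0.455 to 0.536. Holding the denominator at 18 months gives 8.18/18 = 0.454 to 10.15/18 = 0.564, which changes little.

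**Dilution.** Let s be the share of treatment-arm post visits that come from second-wave clinicians. Control visits are unexposed whenever they occur, so with a constant additive effect:

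expected coefficient = true effect × (1 − s × f)

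Assume even visit rates, earlier visits for all second-wave clinicians, and access on the approval date:

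- s = 0: no dilution
- s = 10%: 0.10 × 0.455 to 0.10 × 0.536 = 4.6% to 5.4%
- s = 25%: 11.4% to 13.4%
- s = 50%: 22.8% to 26.8%

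Access one to three months after approval raises f to between 0.511 and 0.694. The 25% case then becomes 0.25 × 0.511 = 12.8% to 0.25 × 0.694 = 17.3%. If every second-wave clinician was a new hire, f = 0 and there is no dilution.

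**Simulation check of the mechanism (all inputs assumed).** With a true effect of 0.10, 30% of clinicians in the second wave in each arm, and joining at month 9 of 18, the formula predicts 0.10 × (1 − 0.30 × 0.50) = 0.085. Go-live coding gave 0.0845; coding by each clinician's own exposure date, with month indicators, gave 0.104. In a separate set, go-live coding gave 0.097, 0.090 and 0.078 at shares of 10%, 25% and 50%. When the second wave was all new hires (25% share), it gave 0.100. The separate set absorbed clinician effects instead of fitting the SAP's random effects, so these runs support the direction and approximate size, not exact figures for the SAP model.

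**Simulation check of the remedy (all inputs assumed).** The hard case is unequal second-wave shares (40% treatment, 10% control) with a non-linear time trend, again with a true effect of 0.10:

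- Dropping interim visits with one linear time term: 0.105 and 0.106
- Coding interim visits as pre with one linear time term: between 0.092 and 0.114 across the checks
- Month indicators: 0.099 to 0.100
- First wave only: 0.099 to 0.100

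**The case against.** The strongest reply is that the harm rests on facts the documents do not supply. The amendment entry shows that a second recruitment was approved, not that anyone joined, was analysed, or had earlier visits. Its stated reason, provider turnover, suggests that some recruits were replacements with no interim visits. All of this stands, and it keeps the size hypothetical. It does not remove the point: the Protocol's eligibility criteria set no hire-date limit, and its recruitment section draws on clinic provider lists, clinic presentations and previous collaborators, so existing clinicians could also join.

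Three narrower replies do not hold.

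- *Participating clinician might mean only visits after enrolment.* The SAP counts baseline visits from late 2019 as participating clinicians' visits, whereas the change to individual randomisation is dated 9/16/20.
- *The access date might be the clinician's own.* The SAP ties it to October/November 2019 plus one year, which cannot describe someone recruited after August 2021.
- *Intention-to-treat might cover it.* That principle governs time after randomisation; these visits come before it.

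It could also be said that an amendment log should not be set against current text. Here the entry serves only as the date of an event, not as a conflicting rule.

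A reader might infer that the trial's estimates were in fact biased, or that any null result is explained by this. The documents support neither inference.

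**Conclusion.** The point holds as a defect in the stated rule. The SAP's post indicator, "c) pre-/post-OneSheet go-live", gives a wrong exposure code for any second-wave treatment clinician with visits between go-live and randomisation. About 46–54% of the post period precedes the approval of the second recruitment. The resulting dilution is toward zero: nil at a zero share, about 5% at an assumed 10%, 11–13% at an assumed 25%, and 23–27% at an assumed 50%.

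These percentages assume even visit rates, earlier visits for all second-wave clinicians, a constant effect and access on the approval date. Actual misclassification is not shown, and there is none if second-wave clinicians were excluded, coded by their own date, or had no interim visits. The point should be fixed, with medium confidence that it affected the analysis at all.

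**What to change.** First, state in the SAP how second-wave clinicians were handled, and report the number of clinicians by wave and arm. If they were excluded or already coded by their own date, correct the SAP text; that takes one or two sentences and no re-analysis. If they had no visits before joining, say so; the estimates are unaffected.

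If interim visits were included, then for second-wave clinicians in both arms:

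- start the post period at the clinician's own randomisation date;
- drop visits between go-live and that date;
- include calendar month or quarter indicators, not a single linear time term. The window runs from late 2019 to May 2022 and the Protocol itself refers to covid-19 changes in clinic operations, so a straight-line trend is doubtful.

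Do not recode interim visits as pre with only a linear adjustment: in the checks above this missed the true effect in both directions, and an upward error could create an apparent effect.

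Report a first-wave-only sensitivity analysis alongside. The cost is re-coding one variable from randomisation dates that the study should hold, re-running six models, and slightly fewer analysed visits.

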Each outcome was set to 1 if the patient met the lookback criteria outlined above (e.g., 90 days for pain-related goals, PEG, and PDMP; 1 year for UDS, seven days for MOUD and Naloxone), or if the provider completed a given task one week following the visit (a 7-day grace period). For PDMP review, there was no one-week grace period because PDMP review is recommended by the CDC (and mandated by many states) to occur at the time of opioid prescribing.

The outcomes of pain-related pain and function goals and PEG assessments were evaluated for all patients with chronic pain, while the CDC recommendations for PDMP checking, UDS review, MOUD ordering, and Naloxone ordering only apply to patients on long-term opioid therapy (LTOT). We identified visits for patients on LTOT as those involving an opioid analgesic prescription lasting at least 28 days, per the Agency for Healthcare Research and Quality's CDS Connect recommendation for assessing opioid therapy (Agency for Healthcare Research and Quality, 2018).

As an example outcome, if a patient on LTOT had not had a UDS result in the last calendar year, but the provider ordered a UDS on the day of the visit, the outcome would be set to 1 (guideline-concordant). Similarly, if the patient had a UDS result in the last calendar year, the outcome would be set to 1 because at the time of the visit, the clinician was concordant with the CDC guideline recommendations for UDS review. If both a) a UDS had not been completed in the last year and b) the clinician did not order a UDS within one week of the visit, the outcome would be set to 0 (non-concordant).

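### The SAP states neither the random-effects structure nor the standard-error type; if the model was a clinician intercept with model-based errors, the treatment-by-post tests are miscalibrated, most of all for UDS

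*SAP*

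**What the plan says.** The protocol's Lay Summary and Research Design section randomises enrolled providers to OneSheet or control, and the IRB Amendments table records the move from clinic-level to individual randomisation. The SAP analyses visits, 12 months before go-live and 18 months after, and takes them broadly: "any visit that a qualifying patient has with a participating primary care clinician was considered as a qualifying visit for the trial". For UDS, PDMP, MOUD and naloxone, the Outcomes text narrows this to long-term opioid therapy visits, defined as "those involving an opioid analgesic prescription lasting at least 28 days".

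The six binary outcomes use lookback windows: "90 days for pain-related goals, PEG, and PDMP; 1 year for UDS, seven days for MOUD and Naloxone". All but PDMP also have a 7-day grace period after the visit. The worked example for UDS states the consequence: "if the patient had a UDS result in the last calendar year, the outcome would be set to 1".

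The Statistical Analysis paragraph gives the model: "we used a multi-level linear probability model including patient demographics, clinician random effects, and indicator variables for a) site", with indicators for arm and for period. It adds the arm-by-period interaction, "the coefficient for which estimates the causal effect of OneSheet on our outcomes of interest". Tests are two-sided at 0.05. The paragraph names no standard-error type, no patient term and no clinician-by-period term. It lists fixest and lme4 without saying which produced the reported inference. The work was complete before the SAP's date of March 2024: "Data analyses were performed from November 2022 to September 2023".

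**The concern.** The interaction is a difference in pre/post changes between arms. A clinician intercept is common to both periods, so it largely drops out of each clinician's change and does little to protect that contrast. What remains is correlation among visits within a period, and the SAP's scoring rules create it: one urine screen makes a patient's visits concordant for the next year, and one PEG or PDMP check does so for 90 days. An intercept-only model with model-based errors treats those visits as independent given the clinician.

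At stake is the precision claimed for the one coefficient that the SAP calls causal. Under that combination its p-values and confidence intervals would not have the stated 5% and 95% properties, and the error would differ by outcome. This is separate from multiplicity across the six outcomes.

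**Working it through.** **Figure to check.** The plan's only relevant figure is the two-sided 0.05 threshold. It gives no power calculation, intraclass correlation, visit count or visit spacing, so the check is whether 0.05 is the real test size under no effect.

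**Step 1: visits that one action can score.** At regular spacing *g* days and window *W*, the count is floor(*W*/*g*) + 1.

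| Spacing (days, assumed) | UDS, W = 365 | Goals, PEG, PDMP, W = 90 |
|---|---|---|
| 28 | 13 + 1 = 14 | 3 + 1 = 4 |
| 60 | 6 + 1 = 7 | 1 + 1 = 2 |
| 90 | 4 + 1 = 5 | 1 + 1 = 2 |
| 180 | 2 + 1 = 3 | 0 + 1 = 1 |

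The count of 14 requires a qualifying opioid-prescription visit every 28 days for a year.

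**Step 2: null simulation, intercept-only model, model-based z test.** Inputs from the documents: windows, grace rule, 12 and 18 months, clinician as randomised unit, 0.05. Assumed: 100 clinicians 1:1 (six settings repeated with 40 or with 250, the protocol's enrolment figure), clinician logit SD 0.5, 5 stable patients per clinician or 15 with turnover, and the spacings and action rates shown. Site and demographics were not simulated. There were 1,000 trials per setting (margin about ±1.4 points near 5%, ±2 to 3 at higher rates) and 67 settings.

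| Outcome and assumption | Type I error |
|---|---|
| UDS, ordered independently of due date (0.1 per visit), near-regular 28/60/90/180 days | 47/28/24/11% |
| UDS, ordered only when due (0.5), same spacings | 20/16/14/9% |
| UDS, 180 days with strong patient differences; or 90% of due tests ordered | 5-7% |
| Goals/PEG, near-regular 28/60/90/120/180 days | 26/14/10/7/6% |
| Goals/PEG, strong patient differences, near-regular 60/90 days | 7/5% |
| PDMP, check rate 0.3, near-regular 28/60/90/180 days | 23/13/11/4% |
| PDMP, check rate 0.9, same spacings | 9/9/6/4% |
| MOUD/naloxone, near-regular 28 or 60 days | 4-5% |
| MOUD/naloxone, random spacing 28 days; 60 or 90 days | 14%; 8% |

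UDS was at 10% or more in 22 of 27 settings. The high PDMP rate is included because the SAP says "PDMP review is recommended by the CDC (and mandated by many states) to occur at the time of opioid prescribing".

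**Step 3: second simulation, different assumptions.** Clinician logit SD was 0.7, patient SD 0 to 4, with 3 to 30 patients per clinician and 1,000 trials per cell. The benchmark with no overlap (7-day window, regular quarterly visits, no patient differences) gave 4.7%, so the set-up reproduces 5% when it should. UDS exceeded 5% in 20 of 21 cells and had the highest rate of the outcomes run in every cell. The rejection rate should follow from r = true SD / model-based SE as 2[1 − Φ(1.96/r)], and it does:

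| Cell | r | Formula | Simulated |
|---|---|---|---|
| UDS, 30-day visits, patient SD 1 | 2.18 | 36.9% | 39.1% |
| UDS, quarterly, no patient differences | 1.52 | 19.7% | 19.3% |
| UDS, every 180 days, patient SD 1 | 1.08 | 7.0% | 7.2% |
| UDS, quarterly, static panel, patient SD 3 | 0.97 | 4.3% | 4.4% |
| MOUD, quarterly, static panel, patient SD 3 | 0.73 | 0.7% | 0.7% |

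PEG/goals fell to 3.6% and 1.6% in two cells, so the error can also be conservative. MOUD rose to 7.7% and 12.4% with panel turnover. Clinician-by-period drift (SD 0.3) gave UDS 21.9%, PEG 15.0% and MOUD 10.4%.

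**Step 4: what restores the size.**
- Clinician-clustered errors: 3.7-6.7% (CR1, t with J − 2 df) and 3.6-6.5% (CR2) in all 67 settings; 3.6-6.5% in the second simulation.
- t-test on clinician-level changes: 3.8-6.4%.
- Clinician random slope on post, still with model-based errors (500 trials, margin about ±1.9 points near 5%): UDS at near-regular 28/60/90 days fell from 43/32/18% to 5.0/6.0/3.8%; UDS ordered only when due, 60 days, from 19% to 5.4%; PEG at near-regular 28 days from 27% to 4.4%, and at random 60 days from 23% to 6.0%. A further run of 300 trials per setting gave 5-8% for UDS and PEG.
- Patient plus clinician intercepts, model-based errors: PEG 20.2% and 27.8%, UDS 33.2%, 52.4% and 17.2% in the five settings tried, all at 28- or 60-day spacing.

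**The case against.** The strongest reply is that the SAP may describe a sound analysis too briefly. Its phrase for the clinician effects is plural and never says intercept, so a random slope on period fits the wording, and Step 4 shows that such a model is about nominal even with model-based errors. Listing fixest leaves clinician-clustered errors open too. This stands: two unknowns must both be adverse before the tests fail, and the documents settle neither.

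It also stands that every magnitude rests on assumed inputs. Counts such as 22 of 27 describe a chosen grid, not a probability, and 47% is one corner of it.

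A reader might infer more than the documents support:
- That the trial's reported p-values are wrong. The documents do not show which model or errors produced them.
- That all six outcomes share the problem equally. They do not: the 7-day outcomes have little overlap, and some tests are conservative.
- That the lookback is the sole cause. Panel turnover and clinician drift over time also contribute.
- That one urine screen did score 14 visits. Visit spacing is not given, and only prescription visits of the stated length count.

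None of this removes the gap. A single clinician intercept is the most natural reading of the sentence as written, and under it the error bars on the key coefficient are unreliable.

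**Conclusion.** The point holds in conditional form. The omission is certain; the miscalibration follows only if an intercept-only model was combined with model-based errors. In that case UDS is the most exposed outcome, and goals, PEG and PDMP are usually affected to a lesser degree. MOUD and naloxone are inflated only if visits bunch, panels turn over or clinicians drift. The direction for the shorter windows cannot be predicted without the data, because stable patient differences in a static panel push the tests towards conservatism. The point should be fixed, with medium confidence that reported results are affected. If either clustered errors or a clinician slope on period was used, only the reporting gap remains.

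**What to change.** Add to the Statistical Analysis paragraph: (1) the exact random-effects structure, including whether there is a clinician slope on period; (2) the standard-error type, any small-sample correction, and which package produced the reported inference.

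Base every treatment-by-post p-value and confidence interval on one named method from Step 4 that restored nominal size; clinician-clustered errors (CR1 with a t reference and CR2 performed alike) are the most direct. Adding only a patient random intercept should not be relied on.

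Cost: a sentence or two if an adequate method was already used. Otherwise it is a re-run of existing code on existing data, with no change to outcome definitions or trial conduct. The downside is usually wider confidence intervals, most of all for UDS.
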